11.2.2 Secondary Efficacy Analyses

The first secondary efficacy analysis will be analyzed using the F-S test (Finkelstein and Schoenfeld 1999). This method compares each subject to every other subject in a pairwise manner following the ranking of the first secondary endpoint (Ordinal Outcome Scale):

- 1) not hospitalized and no limitations of activities;
- 2) not hospitalized, with limitation of activities, home oxygen requirement, or both;
- 3) hospitalized, not requiring supplemental oxygen and no longer requiring ongoing medical care
- 4) hospitalized, not requiring supplemental oxygen but requiring ongoing medical care
- 5) hospitalized, requiring any supplemental oxygen;
- 6) hospitalized, requiring noninvasive ventilation or use of high-flow oxygen devices;
- 7) hospitalized, receiving invasive mechanical ventilation or extracorporeal membrane oxygenation (ECMO);
- 8) MI or stroke diagnosed since randomization
- 9) Death

The F-S test is based on the sum of 'scores' of subjects in the CardiolRx™ group. Where the score is 1, -1 or 0 according to whether the subject is the winner, the loser or tied, respectively, according to the hierarchy above.

In addition, the CardiolRx™ to placebo Win ratio (WR) will be calculated, as described by Pocock.(Pocock et al. 2012) For this statistic, every subject in the CardiolRx™ group is compared to every subject in the placebo group in a pairwise manner following the ranking of the first secondary efficacy endpoint. The WR is the number of pairs with CardiolRx™ subject 'wins' divided by the number of pairs with placebo subject 'wins'. The associated 95% CI will be based on the F-S test statistic to ensure consistency between the CI and the F-S test. A 95%CI for the WR entirely above 1 indicates a better outcome in the CardiolRx™ group.

Changes in hs-troponin and TNF-alpha from baseline to peak elevation during the 28-day treatment period between the two treatment groups will be analyzed using an ANCOVA with the baseline value as covariate.

Treatment effect estimates and 95% confidence intervals will be determined.

To control the family-wise Type I error rate, the Benjamini-Hochberg procedure will be applied to all secondary efficacy analyses.

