10.1.2 Secondary efficacy evaluations

The secondary efficacy parameters are listed in section 4.1.4.

To control the family-wise Type I error rate, the Benjamini-Hochberg procedure will be applied.

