10.1.3 Other efficacy evaluations

Other efficacy parameters are listed in section 4.1.5

The results of the findings for other endpoints are supportive and not confirmatory on their own. Therefore, the effect of the randomly allocated study treatment on the other efficacy endpoints are reported, in addition to measures of effect sizes, standard errors, confidence intervals, with nominal p values, unadjusted for testing multiplicity.

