11 STATISTICAL METHODS

11.1 Sample Size Estimation

Assuming that 19% of patients qualifying for the study in the placebo group would develop one or more primary outcomes, a treatment effect of lowering the event rate by 50% (i.e., only 9.5% of patients treated with CardiolRx™ would experience a primary outcome event, a two-sided alpha of 0.05 and 80% power, 211 patients per group (422 in total) would be required.

Consideration will be given to adjust the sample size just before the interim analysis, should the observed event rate differ from the assumption above. Consideration will also be given to upgrading the Ordinal Outcome Scale first secondary endpoint to be the primary endpoint should the event rate of the current primary endpoint be significantly lower than the above assumption. This would be carried out in a blinded fashion. If the overall primary event rate is lower than $(19 + 9.5)/2 = 14.25\%$, the sample size will be increased to preserve 80% power to detect a 50% relative reduction with a two-sided alpha of 0.05.

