11.4 Statistical Inference

P-value-based claims about the primary efficacy outcome will be based on $p < 0.05$.

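### As designed, the Protocol tests three multiplicity-adjusted secondaries whether or not the primary succeeds, so the chance of a false claim across primary and secondaries exceeds 0.05 (about 0.075 under stated assumptions)

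*Protocol*

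**What the plan says.** - **Primary.** Protocol 11.4: "P-value-based claims about the primary efficacy outcome will be based on" p < 0.05. The sample-size statement in 11.1 shows that this is two-sided and that all of it goes to the primary: "a two-sided alpha of 0.05 and 80% power, 211 patients per group (422 in total) would be required". The primary test is Fisher's exact test (11.2.1).
- **Secondaries.** Section 4.1.4 lists three: the win ratio on the Ordinal Outcome Scale, and the changes to peak in hs-troponin and in TNF-alpha. On multiplicity, 11.2.2 says "To control the family-wise Type I error rate, the Benjamini-Hochberg procedure will be applied to all secondary efficacy analyses". Section 10.1.2 and the synopsis say the same. No level is given for the procedure, and the primary is not part of the family.
- **Other endpoints.** Protocol 10.1.3: "The results of the findings for other endpoints are supportive and not confirmatory on their own". For that reason they get nominal, unadjusted p-values.
- **Link between primary and secondaries.** None. No section makes the secondaries wait for the primary or splits alpha.
- **SAP.** Because the study ended early, the primary events are only listed (9.1.1), the win ratio is not produced (9.2) and no multiplicity adjustment is defined (6.4.1). Testing is limited to marker data (6.2, 6.4), by ANCOVA (9.2).

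**The concern.** The Protocol names family-wise error control as its aim but applies it only inside the secondary family. The primary has its own 0.05 beside that family. If the composite fails, the text still allows a multiplicity-adjusted finding on hs-troponin, TNF-alpha or the win ratio to be put forward. A trial that missed its primary could then be presented as positive on a marker, and the chance of at least one false claim over the four endpoints would exceed the 0.05 applied to the primary. This is a separate matter from which procedure is used within the secondary family: replacing Benjamini-Hochberg with Holm would leave the missing link as it is.

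**Working it through.** **Inputs.** Placebo rate 19%, active rate 9.5%, 211 per group, two-sided 0.05, 80% power (11.1); Fisher's exact test (11.2.1); three secondaries under Benjamini-Hochberg (4.1.4, 11.2.2). Two inputs are assumptions: a level of 0.05 for the secondary family, suggested only by the 95% intervals in 11.2.2, and the correlation between test statistics, for which the documents give nothing.

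**1. The plan's own figure.** Pooled formula with mean rate (0.19 + 0.095)/2 = 0.1425:

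n = [1.960 × √(2 × 0.1425 × 0.8575) + 0.842 × √(0.19 × 0.81 + 0.095 × 0.905)]² / 0.095² = 211.4 per group.

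This matches the stated 211 (212 if rounded up; power at 211 is 0.799). A one-sided 0.05 would give 167. The design therefore spends the whole two-sided 0.05 on the primary and reserves nothing for the secondaries.

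**2. Actual size of the primary test.** Full enumeration of Fisher's test at 211 per arm gives a size of 0.0366 at a 14.25% rate in both arms, 0.0380 at 19% and 0.0342 at 9.5%.

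**3. No endpoint has an effect, independent tests.** Benjamini-Hochberg at 0.05 then rejects at least one secondary with probability 0.05.

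- Primary of exact size 0.05: 1 − 0.95 × 0.95 = 0.0975.
- Fisher, 14.25% rate: 1 − 0.9634 × 0.95 = 0.0848.
- Fisher, 19% rate: 1 − 0.9620 × 0.95 = 0.0861.

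**4. No endpoint has an effect, correlated tests.** Simulation of four equally correlated normal statistics (at least one million replicates per case), giving P(at least one false claim):

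| Correlation | Primary of size 0.05 | Fisher, size 0.0366 |
|---|---|---|
| 0 | 0.098 | 0.085 |
| 0.3 | 0.093 | 0.081 |
| 0.5 | 0.086 | 0.075 |
| 0.8 | 0.068 | 0.058 |

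At correlation 0.5 with Fisher, the part with a failed primary and at least one significant secondary is 0.0747 − 0.0366 = 0.038. That counts both directions; about half, 0.019, favours the drug.

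**5. One secondary truly works; the primary and the other two secondaries do not.** Benjamini-Hochberg then tests the two null secondaries at up to 2/3 and 3/3 of 0.05. With independent tests, P(a false secondary claim) = 1 − (1 − 0.0333)² + (0.05 − 0.0333)² = 0.0658. Adding the primary gives 1 − 0.95 × 0.9342 = 0.1125, or 1 − 0.9634 × 0.9342 = 0.100 with the Fisher size. The figures in step 4 are therefore not a worst case.

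**6. With a gate.** If the primary is null, every claim needs a false primary rejection first. The chance of any false claim is then at most 0.05 (about 0.037 with Fisher), whatever is true of the secondaries. If the primary and one secondary truly work, the gate is passed and 0.0658 remains for the other two, because Benjamini-Hochberg controls the false discovery rate and not the family-wise rate.

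**The case against.** - **No overall promise.** The family-wise sentence covers the secondaries only. A reader might infer that the Protocol guarantees 0.05 over all four endpoints and breaks that guarantee. It gives no such guarantee, and treating primary and secondaries as separate families is a weak choice rather than a contradiction. This stands.
- **Status of the secondaries.** No section calls them confirmatory, and 11.4 ties p-value claims to the primary alone. One could read the secondaries as supporting no claim after a failed primary. Against that, 10.1.3 leaves the other endpoints unadjusted precisely because they are not confirmatory, which implies a different role for adjusted ones. Section 11.2.2 also reads a win-ratio interval above 1 as a better outcome without reference to the primary. The inference is reasonable, but it remains an inference.
- **Choice of number.** It is tempting to quote 0.086 as the error rate. With correlation 0.5 that figure needs a primary test of exact size 0.05, and the planned Fisher test is smaller. The correlation has no source in the documents. A range is the honest form.
- **Overtaken by the SAP.** The SAP no longer tests the primary or the win ratio, drops the Benjamini-Hochberg family, and omits TNF-alpha from the marker list in 9.2. Of the four tests above only hs-troponin remains. None of these error rates describes the analysis to be run, and a gate on an untested primary would do nothing there. This stands and limits the scope.

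**Conclusion.** The point holds for the Protocol as designed. The primary takes the full two-sided 0.05, the three secondaries form a separate adjusted family, and nothing links them. If no endpoint has an effect, the chance of at least one false claim is about 0.075 with the planned Fisher test at correlation 0.5 (0.058 to 0.085 over correlations 0.8 to 0), or 0.086 (0.068 to 0.098) with a primary test of exact size 0.05. Every case examined with a null primary exceeds 0.05. The size rests on three assumptions: a 0.05 level for the secondaries, their use to support claims, and the correlation. It does not show a broken explicit promise, and it does not carry over to the SAP. The change should be made, since it is cheap and removes a route by which a failed primary could be followed by a marker claim.

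**What to change.** **Protocol 11.2.2, 10.1.2 and synopsis.** State that the secondaries are tested for claims only if the primary endpoint is significant at two-sided 0.05. Define the primary endpoint here as the composite, or whichever endpoint is primary after any blinded upgrade under 11.1. Otherwise report secondary estimates, 95% confidence intervals and nominal p-values as exploratory, in the terms 10.1.3 already uses. State the level for the secondary family, and replace Benjamini-Hochberg with a family-wise procedure such as Holm or a fixed sequence. The gate covers the case of a null primary, and the family-wise procedure covers the case of an effective one.

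**SAP 6.4.1 and 9.2.** Label the marker ANCOVA comparisons, including hs-troponin, as exploratory with nominal p-values. SAP section 10, which says that no inferential testing will be done, should be aligned with the exception in 6.4.

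**Cost.** A few sentences, with no added patients or data. The price is that no secondary claim is possible after a failed primary, though the estimates are still reported. Holm or a fixed sequence may also give somewhat less power among the secondaries than Benjamini-Hochberg.

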11.2.3 Other Efficacy and Safety Analyses

The differences in continuous outcomes from baseline to 4 weeks post randomization between the two treatment groups will be analyzed using an ANCOVA. Treatment effect estimates and 95% confidence intervals will be determined.

Binary outcomes will be compared using Fisher's Exact test. The differences in proportions experiencing these outcomes will be estimated, along with 95% confidence intervals.

The elevation of hs-troponin, NT-proBNP, D-dimer and inflammatory markers over time from baseline to Day 7 will be compared using a ROC-AUC analysis, including data from all time points.

Win ratios for Ordinal Outcome Scale endpoint to 60 days after randomization will be analyzed as described above for the first secondary efficacy endpoint (Section 11.2.2).

Standard tests of the overall difference between treatment groups will be performed for the C-SSRS and the PICQ .

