- Patient Impression of Change Questionnaire (PICQ) at Day 28 and at Day 60
- Development of severe lymphopenia, defined as < 1000 cells/microliter within 28 days post randomization
- Change in (elevation of) hs-troponin, NT-proBNP, D-dimer and in inflammatory markers (hs-CRP, ferritin, TNF-alpha, IL-1 beta, IL-6, IL-10) from baseline to Day 7 [area under the curve (AUC)]
- Change from baseline to peak elevation of NT-proBNP, D-dimer and in inflammatory markers (hs-CRP, ferritin, TNF-alpha, IL-1 beta, IL-6, IL-10) during the 28-day treatment period
- Change from baseline to peak elevation of lactate dehydrogenase (LDH) during the 28-day treatment period
- Difference in cardiac magnetic resonance imaging (CMR) parameters between the two treatment groups after 4 weeks of study treatment (subset of patients at selected sites)

Primary Safety Objective

To evaluate the safety of CardiolRx™ in patients with COVID-19 infection

Primary Safety Endpoint

Number of serious adverse events (SAEs) and adverse events (AEs) during the 60-day study period in each group

Secondary Safety Endpoints:

Changes in C-SSRS, blood chemistry and hematology parameters (including lymphocyte count), ALT, AST, bilirubin, eGFR, creatinine, international normalized ratio (INR) as well as QTc interval

Number of Patients:

422 patients will be randomized (211 to CardiolRx™ and 211 to placebo)

Scheduled Duration of Study:

Estimated 9 months recruitment, 2 months follow-up, data cleaning 2 months and 2 months statistical analysis and reporting;

If all timelines are met, the total duration of the study will be approx. 15 months.

Design & Methodology

Multi-center, double-blind, randomized, placebo-controlled, parallel group design. 1:1 randomization.

Screening (Day 0-1): Patients hospitalized for COVID-19 will be screened. If patient consent can be obtained, baseline assessments will be carried out: Physical examination (including vital signs),

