4.1.5 Other Efficacy Parameters

Other efficacy parameters include the following:

- Percentage of patients developing any one of the primary endpoint components within 60 days post randomization
- CV mortality at 28 days post randomization
- Percentage of patients requiring dialysis within 28 days post randomization
- Win ratio of the Ordinal Outcome Scale endpoint within 60 days of randomization
- PICQ at Day 28 and at Day 60
- Development of severe lymphopenia, defined as < 1000 cells/ microliter within 28 days post randomization
- Change in (elevation of) hs-troponin, NT-proBNP, D-dimer and in inflammatory markers (hs-CRP, ferritin, TNF-alpha, IL-1 beta, IL-6, IL-10) from baseline to Day 7 (AUC)
- Change from baseline to peak elevation of NT-proBNP, D-dimer and in inflammatory markers (hs-CRP, ferritin, IL-1 beta, IL-6, IL-10) during the 28-day treatment period
- Change from baseline to peak elevation of LDH during the 28-day treatment period
- Difference in CMR parameters: LVEF, LVEDV, LVESV, LAESV, ECV, GLS, LV mass, LGE extent and edema between the two treatment groups after 4 weeks of study treatment (in a subset of patients at selected sites).

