6.2 Initial procedures

On Days 3, 5, and 7 vital signs and an ECG will be recorded at 5 hours post morning dose (time window 3.5 – 6 hours) with QTc interval assessed. If the QTc interval is > 500 msec or shows an increase of > 60 msec from baseline, the study medication must be stopped immediately.

In addition to prolongation of the QTc, careful observation is required to detect other ADRs and DDIs. Because CardiolRx™, inhibits a number of CYP and uridine diphosphate glucuronosyl transferase (UGT) enzymes, the metabolism of other drugs may be impaired, thereby resulting in increased concomitant drug blood levels; therefore, new symptoms may represent toxicity from a concomitant medication that had previously been well tolerated. For more detailed discussion, see section 6.3 of the IB.

In addition, to aid investigators in screening concomitant medications for risk of DDIs, a table of medications that serve as substrate for certain enzyme isoforms inhibited by CardiolRx™ has been prepared (Appendix 17.10).

Frozen samples will be retained for central analysis of CBD levels, hs-troponin, NT-proBNP, D-dimer as well as inflammatory markers (hs-CRP, ferritin, TNF-alpha, IL-1 beta, IL-6, IL-10) and additional parameters of interest every two days until Day 7 as well as on Day 28.

If the patient is discharged before Day 7, the assessments up to Day 7 will be carried out as out-patient or home visits.

After Day 7, all remaining scheduled assessments will be carried out during out-patient visits.

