### 9.2 Secondary Efficacy Analyses

Due to the early termination of the study the Win Ratio of the Ordinal Outcome scale will not be generated. Ordinal outcome scale scores will be listed and summarized for each visit.

The change from baseline in each biomarker (hs-troponin, NT-proBNP, D-dimer) and inflammatory marker (hs-CRP, ferritin, IL-1 beta, IL-6, IL-10) over time will be summarized at each time point and graphically displayed. After review of the profiles over time, the following parameters may be calculated.

Emax 7	Maximum post-baseline change* (baseline-corrected change) up to the time of the Day 7 assessment; reported to 2 decimal places.
Emax 28	Maximum post-baseline change* (baseline-corrected change) up to the time of the Day 28 assessment; reported to 2 decimal places.
AUEC0-7	Area under the change from baseline curve from time zero to the Day 7

AUEC0-28	assessment; calculated using the linear trapezoidal rule; reported to 3 significant figures.
	Area under the change from baseline curve from time zero to the Day 28 assessment; calculated using the linear trapezoidal rule; reported to 3 significant figures.

\*maximum post-baseline change will be positive for biomarkers that increase relative to baseline over the time interval; or negative for those that decrease relative to baseline.

Assumptions for AUEC calculation:

- Time points other than pre-dose will use actual time point instead of nominal time points. If actual assessment time is missing the nominal time will be used.
- Values missing at time points after baseline and prior to last time point in the interval will not be imputed.
- If data at last time point is missing, AUEC will be calculated up to latest non-missing time point.
- AUEC calculation will not include unscheduled and repeat measurements.

Comparison of each parameter between the two treatment groups using an ANCOVA with fixed factors for treatment and the baseline value as covariate will be performed.

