## 10 CHANGES TO PLANNED ANALYSES

Due to the early termination of the study no inferential testing will be performed. All summaries will be presented descriptively. Limited scope reporting is described above.

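### Protocol 11.2.3 names a ROC area for an endpoint that is an area under the time curve; the SAP substitutes a fitting measure but leaves it optional, omits TNF-alpha and does not log the change

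*Protocol*

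**What the plan says.** **Endpoint.** Among the other endpoints, the protocol synopsis lists the change in nine markers "from baseline to Day 7 [area under the curve (AUC" (the brackets close after the quoted words). Protocol 4.1.5 and SAP 4.1.5 repeat this with the abbreviation AUC. None of the three mentions ROC.

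**Protocol analysis.** Section 11.2.3 takes "The elevation of hs-troponin, NT-proBNP, D-dimer and inflammatory markers over time from baseline to Day 7" and says that it "will be compared using a ROC-AUC analysis, including data from all time points".

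**Sampling.** Protocol 6.2 has samples kept "every two days until Day 7 as well as on Day 28". With the baseline sample, the laboratory schedule in Appendix 17.2.2 gives four values per patient up to Day 7: baseline and Days 3, 5 and 7.

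**SAP analysis.** Section 9.2 defines AUEC0-7 as "Area under the change from baseline curve from time zero to the Day 7" assessment, "calculated using the linear trapezoidal rule". It compares the arms by ANCOVA with the baseline value as covariate. The section presents AUEC0-7 and its companion parameters as ones that may be derived once the profiles have been reviewed. Its marker list has eight entries.

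**SAP on testing and on changes.** Sections 6.2 and 6.4 drop statistical testing because of early termination, but except the bio- and inflammatory markers. Section 10 drops inferential testing with no exception and adds only: "Limited scope reporting is described above". Section 2 says that departures from the protocol are noted and that the plan is approved before unblinding.

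**The concern.** Two different quantities share the abbreviation AUC. One integrates a marker's course over time and has units of marker level multiplied by time. The other is the probability that a value from one group exceeds a value from the other. It has no time dimension and gives no effect in marker units. Section 11.2.3 names the second for an endpoint defined as the first.

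The SAP moves to the first quantity without naming what it replaces and without committing to calculate it. After early termination the marker comparisons are the only statistical tests left. It should therefore be clear before unblinding which ones will be run, on which markers and by which method.

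**Working it through.** The plan gives no sample size, power or effect size for the Day 7 marker endpoint, so there is no figure to reproduce. The 211 per group belongs to the primary endpoint, and nothing here touches it.

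**Step 1. Endpoint against protocol method.** A ROC analysis needs a state to be separated and one value per unit. The protocol defines no state, classifier or cut-off, and does not say how four values per patient enter.

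**Step 2. The two measures can disagree.** Take invented changes at Days 1 (baseline), 3, 5 and 7, with intervals of 2 days:

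- Profile A (0, 10, 20, 30): 2 × [(0+10)/2 + (10+20)/2 + (20+30)/2] = 10 + 30 + 50 = 90.
- Profile B (0, 30, 20, 10): 2 × [(0+30)/2 + (30+20)/2 + (20+10)/2] = 30 + 50 + 30 = 110.

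The trapezoidal areas differ. The pooled values are the same set {0, 10, 20, 30} in both profiles, so a ROC area over all time points is exactly 0.50. It ignores when the elevation occurred.

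**Step 3. What the wording about all time points could permit.** Suppose the four values per patient were pooled as if independent, with common within-patient correlation ρ. The variance of the comparison is understated by a factor of about 1 + 3ρ, and a nominal two-sided 5% test has true size of about 2 × [1 − Φ(1.96/√(1 + 3ρ))].

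| ρ (assumed) | 1 + 3ρ | Size, formula | Size, simulated (211 per arm) |
|---|---|---|---|
| 0.3 | 1.9 | 16% | 14% |
| 0.5 | 2.5 | 22% | 21% |
| 0.7 | 3.1 | 27% | 25% |
| 0.9 | 3.7 | 31% | 31% |

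The documents give no correlation and do not prescribe pooling. The table shows only why the sentence needed a rule for repeated values.

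**Step 4. Endpoint against SAP method.** SAP 4.1.5 lists nine markers for the Day 7 area: hs-troponin, NT-proBNP, D-dimer, hs-CRP, ferritin, TNF-alpha, IL-1 beta, IL-6 and IL-10. SAP 9.2 lists hs-troponin, NT-proBNP, D-dimer, hs-CRP, ferritin, IL-1 beta, IL-6 and IL-10. 9 − 8 = 1: TNF-alpha has an endpoint but no analysis.

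**Step 5. SAP against itself.** Sections 6.2 and 6.4 keep testing for the markers, and 9.2 specifies the ANCOVA. Section 10 says there is no inferential testing. These cannot all stand. Elsewhere the SAP names what it drops, such as the per-protocol population (5.3), the interim analysis (6.3), subgroups (6.4.2) and the win ratio (9.2). It never mentions the ROC-AUC analysis.

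**The case against.** The strongest reply is that the matter is already handled. SAP 9.2 holds a sound method, and the SAP is due for approval before unblinding. The protocol sentence itself speaks of a course over time, so ROC is probably a slip of terminology. That stands, and it places the remaining work in the SAP.

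Four stronger readings are tempting, and the documents do not support them:

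- *The trial will analyse these endpoints by the wrong method.* The SAP, which governs the reporting, contains no ROC analysis.
- *A ROC area is invalid here in any form.* With treatment arm as the state and one summary value per patient, it equals the Mann-Whitney probability, which is a legitimate rank comparison. Section 11.2.3 does not specify that, and it would still not give the area itself.
- *The method was switched without documentation.* SAP section 2 announces reduced reporting, and 9.2 writes the new method out. The fault is an incomplete list of changes, measured against the SAP's own statement that changes are noted.
- *Parameters will be picked with knowledge of treatment.* The SAP does not say when the profiles are reviewed or whether they are split by arm. The wording leaves that open but does not establish it.

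The error rates in the table rest on assumed correlations and an assumed pooling, so they add nothing to the severity.

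**Conclusion.** The point holds, as a minor one. The method named in Protocol 11.2.3 does not estimate the endpoint, but the SAP already replaces it. What remains is in the SAP: an optional parameter, one of nine markers without an analysis, and a section 10 that omits the replacement and contradicts 6.2, 6.4 and 9.2.

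The consequence is small. Protocol 10.1.3 treats these endpoints as supportive, with nominal unadjusted p values, and no sample size, alpha or primary claim depends on them. The conclusion assumes that AUC in the endpoint means area under the marker-time curve. The phrase running from baseline to Day 7 supports that reading, and SAP 9.2 adopts it.

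**What to change.** Edit the SAP before the blind is broken:

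1. **Section 9.2:** state that AUEC0-7 will be calculated and compared between arms by ANCOVA with baseline as covariate, whatever the observed profiles look like.
2. **Section 9.2:** add TNF-alpha, so that the list matches the nine markers in SAP 4.1.5.
3. **Section 10:** record that AUEC0-7 with ANCOVA replaces the ROC-AUC analysis of Protocol 11.2.3, and that the marker ANCOVAs are the exception to the rule of no inferential testing.

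The cost is a few sentences, plus programming one more marker through the same code. The markers are already sampled at these visits, so the schedule does not change. Rewording Protocol 11.2.3 would need an amendment under Protocol 14.4.2 and would achieve little in a trial that has ended early. The entry in SAP section 10 does the job.
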